8.4.2 Electrocardiograms

The following ECG variables will be reported:

- Heart rate
- PR interval
- RR interval
- QRS duration
- QT interval
- QT corrected for heart rate using Fridericia's formula ($QTcF = QT/RR^{1/3}$)

Observed values and changes from Baseline will be summarized by most recent dose received and RLZ total at scheduled visit and by ECG variable. The number and percentage of participants with normal, abnormal not clinically significant and abnormal clinically significant ECG results will be provided in a shift table from Baseline to worst post-Baseline interpretation during the study.

For the ECG data, all calculations of changes from Baseline and descriptive statistics will be based on the mean of the triplicate assessments at each visit. In the event that there are not 3 available measurements at a given visit, the mean will be calculated based on the number of measurements for which data are provided.

The number and percentage of participants who meet each of the MA criteria outlined in [Section 13.7](#) will be summarized by most recent dose received at any visit (including unscheduled visit).

A listing of electrocardiogram data will be presented, including repeated and unscheduled measurements.

8.4.3 Other safety endpoints

8.4.3.1 Physical examination

Results of abnormalities in physical examination will be listed.

8.4.3.2 Suicidal risk monitoring

Suicidal ideation is defined as an event in any of the following 5 categories:

- 
- 
- 
- 
- 

Suicidal behavior is defined as an event in any of the following 5 categories:

- 
- 

-
-
-

Suicidal behavior or ideation is defined as an event in any of the above 10 categories.

Self-injurious behavior without suicidal intent is corresponding to the response to “Has subject engaged in Non-Suicidal Self-Injurious Behavior?” in questionnaire.

A by-participant listing of the C-SSRS questionnaire data will be provided by treatment group.

8.4.3.3 Assessment and management of Tuberculosis (TB)

By-participant listings of interferon gamma release assay (IGRA) TB test, chest X-ray and TB signs and symptoms questionnaire for TB will be provided.

9 EFFICACY ANALYSES

All efficacy analyses will be performed based on the SS by first dose received as described in [Section 3.6](#), unless specified otherwise. No statistical testing will be performed for efficacy analyses.

9.1 Analysis of the secondary efficacy endpoints

9.1.1 MG-ADL score

The complete list of MG-ADL items and scores are provided in [Table 13–3](#). The total score will be calculated according to the rules set down in [Section 13.3](#).

The MG-ADL total score with associated change from Baseline will be summarized by first dose received and scheduled visit using descriptive statistics.

The above MG-ADL summaries will be repeated for COVID-19 free study participants, where COVID-19 free participants for this SAP exclude:

- Study participants who discontinue treatment due to suspected/confirmed COVID-19 infection (“Confirmed COVID-19” or “Suspected COVID-19” as the relationship to COVID-19 in the COVID-19 Impact eCRF);
- Study participants who discontinue treatment due to non-infection related COVID-19 issues (“General circumstances around COVID-19 without infection” or “other” as the relationship to COVID-19 in the COVID-19 Impact eCRF);
- Study participants have visits affected in treatment period (e.g. visit performed by video call) due to COVID-19 pandemic.

The subgroup summaries will also be performed as specified in [Section 4.9](#).

The MG-ADL total score (excluding ocular items) with associated change from Baseline will be summarized by first dose received and scheduled visit using descriptive statistics.

By-participant listings of MG-ADL values will be provided.

9.1.2 MG-C score

The complete list of MG-C items and scores are provided in [Table 13–2](#). The MG-C total score and MG-C total score (excluding ocular items) will be calculated according to the rules set down in [Section 13.2](#).

The total scores and total score (excluding ocular items) with associated change from Baseline will be summarized by first dose received and scheduled visit using descriptive statistics.

The subgroup summaries (by MuSK+ or AChR+ only) will also be performed as specified in [Section 4.9](#).

By-participant listings of MG-C scores will be provided.

9.1.3 QMG scale

The complete list of QMG items and scores are provided in [Table 13–1](#). Partially missing total scores will be imputed according to the rules set down in [Section 13.1](#).

The QMG total score and QMG total score (excluding ocular items) with associated change from Baseline will be summarized by first dose received and scheduled visit using descriptive statistics.

The subgroup summaries (by MuSK+ or AChR+ only) will also be performed as specified in [Section 4.9](#).

By-participant listings of QMG scores will be provided.

9.1.4 Use of rescue medication (IVIg, PEX) due to worsening

The use of rescue therapy will be identified as a ‘yes’ response to the “Rescue Medication?” question on the Prior and Concomitant Medications CRF and the start date of the rescue therapy is on or after Baseline.

The number of participants in each treatment group with the use of rescue therapy (IVIg, PEX) during the Treatment Period due to worsening will be summarized by first dose received.

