2.3 Study design and conduct

This is a randomized, open-label Phase 3 extension study to evaluate the long-term safety, tolerability, and efficacy of rozanolixizumab (RLZ) in study participants with generalized MG.

Study participants will enter MG0004 from lead-in study MG0003. Study participants in MG0003 who complete the Observation Period or who require rescue medication during the Observation Period will be invited to be rerandomized in MG0004 (except for study participants who opt to receive IVIg or PEX as rescue medication). Study participants who receive IVIg or PEX as rescue therapy during the Observation Period of MG0003 will not be eligible to enroll in MG0004. Study participants who discontinue study medication in MG0003 for any reason other than requiring rescue medication will not be eligible for MG0004.

For any study participant who enrolls in MG0004, the final visit in MG0003 (Visit 14) will serve as the first visit in MG0004 (Visit 1). All activities should be completed at Visit 1 (± 1 week). For criteria pertaining to laboratory measures, the last available value from MG0003 will be used for evaluation of study participant eligibility, as long as the measurement was taken within the last 4 weeks (not older than 32 days) prior to MG0004 Screening. Up to approximately 276 study participants will be enrolled into the lead-in study MG0003. All eligible study participants from MG0003 will be invited to participate in MG0004.

In MG0004, study participants will be randomized in a 1:1 ratio to receive 1 of 2 doses of rozanolixizumab (equivalent to approximately [REDACTED], respectively). Specifically, the following dose arms will be used in the study:

Dose arm 1: equivalent to approximately [REDACTED] rozanolixizumab

- Bodyweight <50kg: dose to be administered [REDACTED]
- Bodyweight ≥ 50 kg and <70kg: dose to be administered [REDACTED]
- Bodyweight ≥ 70 kg and <100kg: dose to be administered [REDACTED]
- Bodyweight ≥ 100 kg: dose to be administered [REDACTED]

Dose arm 2: equivalent to approximately [REDACTED] rozanolixizumab

- Bodyweight <50kg: dose to be administered [REDACTED]
- Bodyweight ≥ 50 kg and <70kg: dose to be administered [REDACTED]
- Bodyweight ≥ 70 kg and <100kg: dose to be administered [REDACTED]
- Bodyweight ≥ 100 kg: dose to be administered [REDACTED]

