6.4 Prior and concomitant medications

The number and percentage of participants taking Prior or Concomitant medications will be summarized using the RS by Anatomical Therapeutic Chemical (ATC) class, presenting as Anatomical Main Group (ATC Level 1), Pharmacological Subgroup (ATC level 3), Preferred Term (PT), treatment group and RLZ total. The number and percentage of participants taking steroids, Immunosuppressants and AChE Inhibitors will be summarized.

Additionally, rescue medications are those that are mentioned in Protocol section 6.5.3 and identified:

- if Rescue Medication is ticked as yes on CRF Concomitant Medication page
- Or PEX as procedure entered on CRF Concomitant Medical Procedure page

The start date of rescue medication should be on or after Baseline. All rescue medications will be summarized using the RS.

Medications classified as prior or concomitant will be listed using the RS. A by-participant listing of participants taking steroids, immunosuppressants and AChE Inhibitors will be listed, including ADD at Baseline, ADD at last study visit and change from Baseline in ADD (See [Section 11.1](#)). A by-participant listing of concomitant procedures will also be listed using the RS. Originally reported dates will be used for listings.

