11.2 Specific analyses for Pharmaceuticals and Medical Devices Agency (PMDA)

The following endpoints will be summarized for participants in Japan only:

- Study participant characteristics, including important PDs (as specified in [Section 5](#))
- Demographics and other baseline characteristics, including medical history, prior and concomitant medications (as specified in [Section 6](#))
- Study IMP duration and number of infusions (as specified in [Section 8.1](#))
- Use of rescue medication (IVIg, PEX) due to worsening (as specified in [Section 9.1.4](#))
- MG-ADL total score and change from Baseline (as specified in [Section 9.1.1](#))
- TEAE Summaries (as specified in [Section 8.2.2](#))
 - TEAE overview
 - The number, percentage of participants and frequency of the following TEAEs will be summarized by SOC, HLT, PT, and by most recent dose prior to onset of TEAEs and RLZ total
 - Any TEAEs
 - Any TEAEs by maximum intensity (mild, moderate and severe)
 - Any TEAEs by relationship
 - Serious TEAE
 - Participant discontinuation due to TEAEs
 - Permanent withdrawal of IMP due to TEAEs
- ADA summaries (as specified in [Section 10.3.2](#)):
 - Number and percentage of participants with positive, negative, missing or inconclusive sample ADA status at the time of each visit and RLZ total will be summarized by treatment group and RLZ total.
 - Number and percentage of participants in each of the ADA classifications presented in [Table 10-1](#) will be summarized by treatment group and RLZ total.

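### SAP 9.1.4 finds rescue use from the medications CRF page only, while SAP 6.4 also counts plasma exchange entered as a procedure, so the secondary endpoint can miss participants rescued by plasma exchange alone

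*SAP*

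**What the plan says.** Protocol 6.5.3 defines rescue therapy as IVIg or PEX. SAP 2.2.2.1 lists its use, yes or no, as one of four secondary efficacy endpoints.

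Two sections of the current SAP say how rescue is found in the data.

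- **SAP 9.1.4**, the endpoint analysis, requires a yes to the rescue-medication "question on the Prior and Concomitant Medications CRF and the start date of the rescue therapy is on or after Baseline". It then counts participants in each group "with the use of rescue therapy (IVIg, PEX) during the Treatment Period due to worsening will be summarized by first dose received". Under SAP 9 this is done on the Safety Set.
- **SAP 6.4**, prior and concomitant medications, ties rescue to Protocol 6.5.3 and accepts either of two records starting on or after Baseline. One is the tick on the medications page. The other is "Or PEX as procedure entered on CRF Concomitant Medical Procedure page". It adds: "All rescue medications will be summarized using the RS". For procedures it adds: "A by-participant listing of concomitant procedures will also be listed using the RS".

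SAP 11.2 repeats "Use of rescue medication (IVIg, PEX) due to worsening" for participants in Japan and points to 9.1.4 for the method.

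**The concern.** PEX is one of the endpoint's two components, and it is a procedure rather than a drug. Section 6.4 allows for that by naming the procedures page as an alternative source. Section 9.1.4 gives a complete rule of its own, leaves that page out and does not point to 6.4. A programmer who follows 9.1.4 as written would not look at the procedures page, and a participant whose only qualifying rescue was recorded there would be reported as not rescued.

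The endpoint has no model or test behind it, so the descriptive count is the whole result. The same omission passes to the Japan-only summary.

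**Working it through.** The documents give no rescue count or rate, so there is no planned figure to reproduce. The check compares the two rules and then sizes one missed participant.

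**Step 1: the rules side by side.** Let T be a yes tick on the medications page and P be PEX entered on the procedures page, each starting on or after Baseline. I take the medications page named in 6.4 and the one named in 9.1.4 to be the same page.

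- Sources under 9.1.4: T
- Sources under 6.4: T or P

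**Step 2: apply the same limits to both.** Let L be the 9.1.4 limits: Safety Set, Treatment Period, worsening.

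- Counted by 9.1.4: participants with a T record within L
- Counted with the 6.4 sources under the same limits: participants with a T or P record within L
- Difference, m: participants with a P record within L and no T record within L

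The first group lies inside the second, so m is zero or positive.

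**Step 3: who falls in the gap.**

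| Qualifying record in the Treatment Period | 9.1.4 | 6.4 sources |
|---|---|---|
| IVIg ticked | rescued | rescued |
| PEX ticked on the medications page | rescued | rescued |
| PEX on the procedures page and a ticked IVIg or PEX | rescued | rescued |
| PEX on the procedures page only | not rescued | rescued |

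Only the last row is affected. The value of m depends on how sites enter PEX, which the documents do not show. It is zero if every PEX is also ticked on the medications page. It equals all participants rescued by PEX alone if PEX is entered only as a procedure.

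**Step 4: size per missed participant.** The fall in an arm's rescue rate is m/n.

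- Ceiling for n: the maximum of 240 (SAP 3.9), split 1:1 (SAP 2.3), gives 240/2 = 120.
- m = 1, n = 120: 1/120 = 0.83 percentage points.
- Arms may be smaller, because entry to MG0004 ends at a site once MG0007 is approved there (SAP 2.4). For assumed arms of 60 and 30, 1/60 = 1.7 points and 1/30 = 3.3 points.

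The documents give no number of participants in Japan, so I put no figure on that summary.

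**The case against.** The strongest reply is that the intended definition is already in the SAP. Section 6.4 says what rescue is and includes PEX from the procedures page, and 9.1.4 names PEX twice. A sensible programmer would probably apply 6.4, which would make this a missing cross-reference. The intent is indeed clear. But 9.1.4 states its own identification rule without mentioning 6.4, while the neighbouring efficacy sections do refer elsewhere for rules they borrow. Two stated rules conflict, and a secondary endpoint should not depend on which one is picked.

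A second reply is that nothing may be lost in practice, because harm requires PEX on the procedures page with no tick on the medications page. That stands: the mismatch is certain and an undercount is not. The alternative in 6.4 does suggest that such entries were foreseen.

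A third is that the consequence is small. This also stands. The SAP says "No statistical testing will be performed for efficacy analyses", and a missed PEX would still appear in the 6.4 rescue summary and the procedures listing.

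Three stronger readings are tempting, and the documents do not support them.

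- *The count must understate true rescue use.* The direction is fixed only relative to the 6.4 sources. Section 9.1.4 does not say how a ticked entry is confirmed as IVIg or PEX, or as given for worsening, so a wrong tick could push the count up.
- *Disagreement between the 6.4 and 9.1.4 outputs would prove the error.* They can differ by design. Section 6.4 uses the Randomized Set and any start on or after Baseline; 9.1.4 uses the Safety Set, the Treatment Period and worsening. Those differences could, however, hide a gap caused by the data source.
- *The treatment comparison is biased.* "In MG0004, study participants will be randomized in a 1:1 ratio to receive 1 of 2 doses of rozanolixizumab", so there is no drug-versus-control contrast, and nothing shows that missed PEX would favour one dose arm.

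**Conclusion.** Wrong as written. SAP 9.1.4 and 6.4 give different source rules for the same event, and the narrower one governs the secondary endpoint and its Japan-only repeat. Followed literally, 9.1.4 misclassifies any participant whose only qualifying rescue is PEX recorded on the procedures page. The number affected is unknown and may be zero. Each such participant lowers the arm's rate by 0.8 points at the ceiling of 120 per arm, and by more if the arms are smaller. This rests on exact 1:1 balance at the maximum sample size and on the two sections meaning the same medications page. The effect is confined to descriptive counts. The point rests on the SAP text in force and not on its change log.

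**What to change.** Amend SAP 9.1.4 as follows.

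1. Identify rescue by the 6.4 definition: a yes tick on the medications page, or PEX on the procedures page, starting on or after Baseline. Refer to 6.4 explicitly so that there is one definition.
2. Keep the existing limits: Safety Set by first dose received, Treatment Period, worsening.
3. State one rule for establishing worsening when PEX comes from the procedures page; neither section does so now. If the page records a reason, use it. If it does not, report the count with and without those cases and flag them in the listing. Counting them by default would drop the worsening limit for one source only.

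SAP 11.2 needs no separate edit, because it takes its method from 9.1.4.

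The cost is a few SAP sentences, one more source dataset in programming, and a review of PEX records found only on the procedures page. No new CRF field is needed. If no reason is recorded, the endpoint is reported as two counts instead of one.

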9.2 Analysis of other efficacy endpoints

9.2.1 MGII

The complete list of MGII items and scores are provided in [Table 13-8](#). The total score and sub-scores will be calculated according to the rules set down in [Section 13.5](#).

The MGII total score and sub-scores (Ocular and a Generalized domain) with associated change from Baseline values will be summarized separately by first dose received and each scheduled visit.

A by-participant listing of MGII scores will be provided.

9.2.2 MG Symptoms PRO

The MG Symptoms PRO scale scores (physical fatigue, muscle weakness fatigability, bulbar symptoms) will be calculated according to the rules set down in [Section 13.4](#). The scale scores with associated change from Baseline values will be summarized by first dose received and each scheduled visit.

By-participant listings of MG Symptoms PRO scores will be provided.

9.2.3 MG-QOL15r

The MG-QOL15r total score is calculated by summing all the individual items. See [Section 13.6](#) for scoring details.

The MGQOL15r total score and change from Baseline values will be summarized by first dose received and each scheduled visit.

A by-participant listings of MG-QOL15r will be provided.

9.2.4 EQ-5D-5L

The EQ-5D-5L essentially consists of 2 pages: the EQ-5D descriptive system and the EQ visual analogue scale (EQ VAS).

A frequency table will be produced to summarize answers provided to each of the 5 dimensions of the EQ-5D descriptive system at each scheduled visit by first dose received. The observed values of EQ VAS scores and change from Baseline will be summarized by first dose received and each scheduled visit. No imputation will be applied on missing item in EQ-5D descriptive system and EQ VAS.

A by-participant listings of EQ-5D-5L will be provided.

9.2.5 MG-ADL responder rate (≥2.0 points improvement from Baseline)

Participants will be classified as responders at a scheduled visit if the MG-ADL total score is at least a 2-point improvement (decrease) from Baseline. Missing data will be imputed using NRI per [Section 4.2.1](#).

The number and percentage of observed responders will be summarized by first dose received and scheduled visit for participants who require rescue treatment during the Observation Period of MG0003 and subsequently enter MG0004 only.

9.2.6 QMG responder rate (≥3.0 points improvement from Baseline)

Participants will be classified as responders at a scheduled visit if the QMG total score is at least a 3-point improvement (decrease) from Baseline. Missing data will be imputed using NRI per [Section 4.2.1](#).

The number and percentage of observed responders will be summarized by first dose received and scheduled visit for participants who require rescue treatment during the Observation Period of MG0003 and subsequently enter MG0004 only.

9.2.7 MG-C responder rate (≥5.0 points improvement from Baseline)

Participants will be classified as responders at a scheduled visit if the MG-C total score is at least a 5-point improvement (decrease) from Baseline. Missing data will be imputed using NRI per [Section 4.2.1](#).

The number and percentage of observed responders will be summarized by first dose received and scheduled visit for participants who require rescue treatment during the Observation Period of MG0003 and subsequently enter MG0004 only.

9.2.8 Minimum symptom expression

Minimum Symptom Expression (MSE) is designed to assess how many participants become free or virtually free of MG symptoms as measured by achieving an MG-ADL total score of 0 or 1 on therapy (Vissing et al. 2020). The total score will be calculated according to the rules set down in [Section 13.3](#).

The number and percentage of participants achieving MSE at scheduled visit will be summarized by first dose received.

10 PHARMACOKINETICS AND PHARMACODYNAMICS

All PK and PD analyses described in this section will be performed by first dose received on the SS, as described in [Section 3.6](#), unless specified otherwise.

10.1 Pharmacokinetics

Individual plasma concentrations of rozanolixizumab will be summarized by most recent dose received and scheduled sampling day using n, arithmetic mean, median, SD, minimum, maximum, geometric mean (geomean) with associated 95% CI, and geometric coefficient of variation (geoCV) (assuming log-normally distributed data).

The following rules will apply for PK data listings and summaries:

- Values below the LLOQ will be reported as BLQ
- Descriptive statistics of concentrations will be calculated if at most 1/3 of the individual data points at a timepoint are missing or are not quantifiable (<LLOQ). Values that are BLQ will be replaced by the numerical value of the LLOQ/2 in this instance. If more than 1/3 of the individual data points at a timepoint are missing or are not quantifiable, then only n, minimum, median and maximum will be presented. The other descriptive statistics will be left blank.
- If n<3, then only the n, minimum and maximum will be presented. If no study participants have data at a given timepoint, then only n=0 will be presented.
- The 95% CI lower and 95% CI upper should be left blank if the SD (or equivalently, the geoCV) is 0
- The geoCV will be calculated using the following formula where SD is the standard deviation from the log-transformed data

$$\text{geoCV}(\%) = \sqrt{\exp(\text{SD}^2) - 1} \times 100.$$

Individual concentrations of rozanolixizumab will be listed by first dose received for the SS and will include the actual sampling time in days relative to the previous dose, most recent dose, the IgG observed at the same visit, the ADA titer observed for the binding assay and the NAb titer for the same visit, IgG and IgG subclasses, and MG-ADL change from baseline for the corresponding visit.

